
2. Background and Rationale
 
For over 4 decades BTX has been used to treat multiple neurologic disorders, such as blepharospasm, strabismus, focal dystonias, muscle spasms and spasticity, axillary hyperhidrosis, migraines and achalasia. It has been also used off-label to treat overactive bladder and urinary incontinence. BTX is a popular treatment for facial wrinkles in both FDA-approved (Glabella) and off-label (crow’s feet, transverse forehead lines, lower face, and neck) indications (1,2).
 
It has also been used recently to relieve a retracted penis (3).
 
Botulinum toxin (BTX) is produced by the gram-positive anaerobic bacterium Clostridium botulinum and is considered among the most potent biologic neurotoxins. Its main mechanism of action is the strong inhibition of acetylcholine (Ach) release at the pre-synaptic cholinergic junction (2). BTX can also affect the autonomic nervous system through its high selectivity for cholinergic synapses which results in targeted blockade of cholinergic transmission, inducing strong relaxation (or may be even paralysis)of striated muscles (4). It has been also reported that BTX may also affect afferent nervous transmission via the inhibition of acetylcholine, adenosine tri-phosphate (ATP),glutamate, nerve growth factor and substance P, and a reduction in the axonal expression of nerve capsaicin and purinergic (P2X) receptors (5).
 
Medical treatment of erectile dysfunction (ED), at its very core, attempts to induce erections by relaxing the smooth muscles of the corpora cavernosa and the lining small blood vessels.
 
The study hypothesis: Evidence has been arising that Botulinum toxin injections can relax smooth muscles fibers in the treatment of obesity and hyperactive bladder. Would a similar effect on cavernosal smooth muscles help in the treatment of erectile dysfunction thus avoiding risks of repeated intra-cavernosal injections with vaso-active substances (e.g. Priapism and penile fibrosis) and surgical treatment options.
	

3. Objectives
 
To evaluate the safety and efficacy of intra-cavernosal Botulinum toxin injection as an alternative line of treatment in patients with erectile dysfunction - not responding to oral PDE5i - through cavernosal smooth muscle relaxation.
	

4. Study Design
 
Prospective, randomized double blind placebo control (RDBPC) study.
	

5. Ethical committee approval
	

Yes

6. Study Methods

Population of study & disease condition

- Married male patients with erectile dysfunction

Inclusion criteria:

- Male patients will be included in the study recruited from Andrology, Sexology & STI's outpatient clinic, Kasr El Aini Hospitals, Cairo University, complaining of ED - not responding to oral PDE5i.
- Unable to develop erections sufficient for intercourse.
- A "No" response on Sexual encounter profile questions (SEP 2 & 3).

Exclusion criteria:

- Single patients.
- Any medical condition in which sexual activity is not advised.
- Any preexisting motor neuron disease (e.g myasthenia gravis).
- Neuropathies.
- Psychological disorders.
- History of reaction to toxin or albumin.
- Infection at the site of injection.
- Patients on aminoglycosides (may increase effect of botulinum toxin), penicillamine, quinine, chloroquine and hydroxychloroquine (may reduce its effect), calcium channel blockers, and blood thinning agents e.g. warfarin or aspirin (may result in bruising)

Methodology in details

Male patients complaining of ED - not responding to oral PDE5i - will be included in the study. All will be subjected for full history taking including assessment of intra-vaginal latency time, general and genital examination including measuring of the visible penile length at its flaccid state from the skin of the suprapubic area to the tip of penis, then stretched flaccid penile length and erected penile length from the pubic bone to the tip of the glans penis, at last penile girth at the mid shaft of the penis will be measured. Penile duplex with a trimix solution (20 ug alprostadil + 1 mg phentolamine + 30 mg papaverine) will be performed to assess erectile function. The patients will be randomized into a treatment group (35 patients) and a control group (35 patients).

All patients will sign an informed consent. A rubber band will be applied to the base of the penis. The skin will be prepped with alcohol swabs followed by intra cavernous injection of the treatment group by 100 units of BTX-A and intra-cavernous injection only with 1 ml saline

in the control group. Direct pressure will be applied for 2 minutes. The rubber band will be removed after 15 minutes.

Patients will be asked to resume their sexual activity using PDE5i on demand 2 weeks after intra-cavernous injection with BTX-A in the treatment group and saline in the control group. Assessment and follow up will be performed 2, 6 and 12 weeks after intra-cavernous injection with BTX-A in the treatment group and saline in the control group including measuring of the visible **penile length** at its flaccid state from the skin of the suprapubic area to the tip of penis, then stretched flaccid penile length and erected penile length from the pubic bone to the tip of the glans penis, **penile girth** at the mid shaft of the penis, assesment of **erectile function** using SEP2 & SEP3 questions, the global assessment question and SHIM questionnaire. Penile duplex with a trimix solution (20 ug alprostadil + 1 mg phentolamine + 30 mg papaverine) will be performed to assess erectile function 2 weeks after intra-cavernous injection with BTX-A in the treatment group and saline in the control group. Intra-vaginal latency time (**IVLT**) will be assessed in each patient 2, 6 and 12 weeks after intra-cavernous injection with BTX-A in the treatment group and saline in the control group. The rational for selecting the minimum 2-weeks waiting period is to give a chance for the BTX-A to reach its maximum effect.

Possible Risks

- Redness, pain and prolonged erections.
- Priapism.
- Possible injection site reactions (e.g. infection, fibrosis, bleeding, bruising or hematoma formation).
- Possible uncommon side effects of BTX-A (e.g. allergic reactions, rash, itching, headache, nausea, diarrhoea, stomach pain, loss of appetite, generalised weakness, muscle weakness, fever, cough, runny nose, flu symptoms, dizziness, drowsiness, anxiety, urinary tract infections, burning/painful urination, or difficulty urinating).

Primary outcomes

1. Comparison of Penile hemodynamics and response to ICI before and 2 weeks after BTX-A injection in the treatment group and saline injection in the control group.
2. Comparison of the SHIM score, SEP2 & SEP 3 questions, and the global assessment question before, 2, 6 and 12 weeks after BTX-A injection in the treatment group and saline injection in the control group.

Secondary outcomes

1. Comparison of penile size before, 2, 6 and 12 weeks after BTX-A injection in the treatment group and saline injection in the control group.

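### Erected length is due at weeks 6 and 12, but the only described in-clinic means of erection is scheduled at baseline and week 2, and no visit states the erection condition

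*Combined protocol and SAP*

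**What the plan says.** All references are to section 6 (Study Methods) of the combined protocol and SAP.

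- **Baseline measurement** (Methodology in details). The genital examination includes "erected penile length from the pubic bone to the tip of the glans penis, at last penile girth at the mid shaft". The duplex comes in the next sentence: "Penile duplex with a trimix solution (20 ug alprostadil + 1 mg phentolamine + 30 mg papaverine) will be performed to assess erectile function".
- **Follow-up measurement** (same subsection). "Assessment and follow up will be performed 2, 6 and 12 weeks after intra-cavernous injection with BTX-A in the treatment group", with the same control-arm visits. The list of assessments again includes visible flaccid length, "then stretched flaccid penile length and erected penile length from the pubic bone to the tip of the glans penis", and girth.
- **Duplex at follow-up.** The trimix duplex "will be performed to assess erectile function 2 weeks after intra-cavernous injection with BTX-A in the treatment group and saline in the control group". None is scheduled at week 6 or 12, and primary outcome 1 gives the same timing (before and week 2).
- **Outcome.** Secondary outcome 1 is "Comparison of penile size before, 2, 6 and 12 weeks after BTX-A injection", with the matching saline comparison. Penile size is not broken down further; that erected length belongs to it follows from the assessment list.
- **Population** (Inclusion criteria). Men do not respond to oral PDE5i and are "Unable to develop erections sufficient for intercourse".
- **PDE5i after injection.** On-demand use from week 2 is described for resuming sexual activity, not for measurement in clinic.

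The protocol does not state a required rigidity, how an erection is obtained for the length measurement, what to do when a man has none at the visit, or whether girth is flaccid or erect.

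**The concern.** Erected length can be measured only in a man who has an erection at the visit. In this population that cannot be presumed, and producing erections is what the treatment is meant to do. Where no induction is scheduled, three things can happen: no value, a value in a partial erection, or a value only in men who have recovered. In the second case erected length partly measures rigidity, so a difference in erectile function could be reported as a difference in size. In the third, the arms are compared within subsets selected by a post-randomisation outcome, and randomisation no longer protects the comparison. If the early values are taken during the duplex, the late values are also not like-for-like with baseline.

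**Working it through.** **1. Schedule, visit by visit**

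| Visit | Erected length due | Trimix duplex scheduled | Erection condition stated for length |
|---|---|---|---|
| Baseline | yes | yes | no |
| Week 2 | yes | yes | no |
| Week 6 | yes | no | no |
| Week 12 | yes | no | no |

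Erected length is due at 4 time points and a described means of erection exists at 2. Of the 3 post-baseline comparisons, 2 have none. The last column matters too: the condition is unspecified at all four visits.

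**2. Possible bias if only men with an erection are measured**

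The documents give no erection rates, so every input here is an assumption. Suppose a share p of each arm is measurable, namely the men with the best erectile response. Suppose also that length correlates r with that response and treatment has no effect on length. With φ the standard normal density and z_p the cut-off exceeded with probability p, the spurious difference (BTX-A minus saline, in SD of length) is

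r × [φ(z_pT)/pT − φ(z_pC)/pC].

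For 60% against 30% measurable: φ/p = 0.3863/0.6 = 0.644 and 0.3477/0.3 = 1.159, a difference of −0.515. Multiplying by r gives the third row below; the other rows follow in the same way.

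| Measurable, BTX-A vs saline | r = 0.1 | r = 0.3 | r = 0.5 |
|---|---|---|---|
| 40% vs 30% | −0.02 | −0.06 | −0.10 |
| 50% vs 30% | −0.04 | −0.11 | −0.18 |
| 60% vs 30% | −0.05 | −0.15 | −0.26 |
| 70% vs 20% | −0.09 | −0.27 | −0.45 |

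In this model the bias is zero if the measurable shares are equal or r = 0, and its sign reverses if r is negative. It does not cover values taken in partial erections.

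**3. Loss of precision**

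The sample size of 70 (35 per arm) is stated without alpha, power, effect size or SD, so it cannot be reproduced. Assuming a two-sample t-test, two-sided alpha 0.05 and 80% power:

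| Men measured, BTX-A vs saline | Detectable difference | Power at 0.68 SD |
|---|---|---|
| 35 vs 35 | 0.68 SD | 80% |
| 28 vs 18 (80% vs 51%) | 0.87 SD | 60% |
| 21 vs 10 (60% vs 29%) | 1.11 SD | 40% |

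The subset sizes are assumptions. These figures show lost precision only; they do not measure the bias.

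**The case against.** The strongest reply is that no passage ties erected length to trimix at any visit. At baseline it sits in the genital examination, ahead of the duplex sentence, and the duplex has its own purpose. A reader might infer that baseline is trimix-induced, that the protocol therefore contradicts itself, and that a change by week 6 or 12 reflects loss of the inducing agent. The documents do not support that as fact. They are silent on the erection condition, and one unwritten method might be used at every visit. This part of the reply stands, and the like-for-like argument is therefore conditional. The reply does not remove the main problem: with no erection method described for weeks 6 and 12, missing, partial or responder-only values remain the expected result in these men.

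A second reply is that week 2 is not clean either. Response to intracavernosal injection is part of primary outcome 1, so whether trimix gives a full erection at week 2 is itself an outcome that BTX-A may change. Baseline adjustment does not cure that. This stands, and the fix below allows for it.

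Third, the consequences may be small. The assumed bias reaches almost zero at its lower end, and the precision examples both build in a gap of about 30 percentage points between arms. Flaccid and stretched length are collected at every visit without needing an erection. This stands as a limit on reach. It does not make the late erect-length comparison interpretable as scheduled.

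**Conclusion.** The point holds in a limited form. The erect-length comparison at weeks 6 and 12 lacks a described means of erection, in men selected for not having adequate ones, and would depend on the treatment outcome. That the early and late values are taken under different conditions is an inference, valid only if the early ones are taken during the duplex. The reach is the erect-length part of one secondary outcome, and girth if taken erect; the primary outcomes and the flaccid and stretched lengths are not affected. The size of the bias is unknown. The range of about −0.02 to −0.45 SD rests wholly on assumed measurable shares (40% vs 30% up to 70% vs 20%) and correlations (0.1 to 0.5). A reader might take it as evidence of material bias, but the documents contain no erection rates that would support that. This is a cheap improvement the sponsor should make, not a threat to the trial's main conclusions.

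**What to change.** Reconcile the measurement schedule with the duplex schedule:

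1. State that erected length is measured during the duplex visits already planned (baseline and week 2), and compare arms at week 2 adjusted for baseline.
2. At those visits measure every man, record the degree of erection, and report the number measurable by arm, because trimix response at week 2 is itself an outcome.
3. Name stretched flaccid length, already taken at every visit, as the size measure for the comparison over 2, 6 and 12 weeks.
4. Drop erected length at weeks 6 and 12 from the between-arm comparison. Any values obtained are descriptive only, shown with the number measured.
5. State whether girth is flaccid or erect, and treat it in the same way.

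The cost is a few sentences in the follow-up schedule and in secondary outcome 1, one extra recorded item (degree of erection), and no added visit or procedure. The downside is that there is no formal erect-length comparison at weeks 6 and 12. No recommendation is made on giving or withholding trimix.
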